- **3.2.9** Pregnant women are excluded from this study because of the potential for teratogenic or abortifacient effects. Because there is an unknown but potential risk of adverse events in nursing infants secondary to treatment of the mother with GSK1120212 and GSK2141795

breastfeeding should be discontinued if the mother is treated with GSK1120212 and GSK2141795.

- **3.2.10** Individuals with a history of a different malignancy are ineligible except for the following circumstances:
 - Individuals with a history of other malignancies are eligible if they have been diseasefree for at least 3 years or are deemed by the investigator to be at low risk for recurrence of that malignancy.
 - Individuals with the following cancers are eligible if diagnosed and treated within the past 3 years: breast cancer *in situ* and basal cell or squamous cell carcinoma of the skin, stage I colon carcinoma confined to a polyp.
- **3.2.11** Any serious and/or unstable pre-existing medical disorder (aside from malignancy exception above), psychiatric disorder, or other conditions that could interfere with subject's safety, obtaining informed consent or compliance to the study procedures, in the opinion of the Investigator.
- **3.2.12** Known Human Immunodeficiency Virus (HIV), Hepatitis B Virus (HBV), or Hepatitis C Virus (HCV) infection (with the exception of chronic or cleared HBV and HCV infection which will be allowed) as these individuals are at increased risk of lethal infections when treated with marrow-suppressive therapy. Appropriate studies will be undertaken in participants receiving combination antiretroviral therapy when indicated.
- **3.2.13** *Required, chronic,* use of drugs that are *strong* inhibitors or inducers of p450 CYP3A4 (see Appendix E for a table of these agents).
- **3.2.14** Have a known immediate or delayed hypersensitivity reaction or idiosyncrasy to drugs chemically related to GSK1120212 and GSK2141795, or excipients or to dimethyl sulfoxide (DMSO).
- **3.2.15** Participants may not use natural herbal products or remedies not approved by the FDA while participating in this study
- **3.2.16** History of interstitial lung disease or pneumonitis.
- 3.2.17 Presence of cardiac metastases
- **3.2.18** Subject with intra-cardiac defibrillators or pacemaker.
- 3.2.19 History of retinal vein occlusion (RVO).
- **3.2.20** History or evidence of cardiovascular risk including any of the following:

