5.3 General Concomitant Medication and Supportive Care Guidelines

The following medications **are prohibited**:

- 1. Other anti-cancer therapy while on treatment in this study. NOTE: megestrol (Megace) if used as appetite stimulant is allowed and palliative radiation therapy can be permitted with the approval of the principal investigator.
- 2. Use of other investigational drugs within 28 days (or five half-lives whichever is shorter; with a minimum of 14 days from the last dose) preceding the first dose of GSK1120212 and GSK2141795during the study.
- 3. All medications in Appendix E are prohibited and those listed in Appendix F are to be used with caution.
- 4. Concurrent treatment with bisphosphonates is permitted; however, treatment must be initiated prior to the first dose of study therapy. Prophylactic use of bisphosphonates in subjects without bone disease is not permitted, except for the treatment of osteoporosis.
- 5. Subjects should abstain from taking any herbal and dietary supplements within 5 half lives (or 14 days if the drug is a potential enzyme inducer) prior to the first dose of either study drug until completion of the follow-up visit.

Because the composition, pharmacokinetics and metabolism of many herbal supplements are unknown, the concurrent use of all herbal supplements is prohibited during the study (including but not limited to St. John's wort, kava, ephedra (ma huang), gingko biloba, dehydroepiandrosterone (DHEA), yohimbe, saw palmetto, or ginseng).

The investigator should contact the study PI before initiating treatment with any herbal preparation.

- 6. Growth factor support is allowed only with the permission of the principal investigator.
- 7. Oral steroids should be used with caution and subjects monitored for steroid-induced hyperglycemia. Short courses (up to a maximum of 14 days) of oral corticosteroids intended to treat study treatment related rash or diarrhea are allowed. Budenoside is recommended for supportive care of diarrhea. Subjects will be instructed to inform the investigator before taking any of these or any other medications. Investigators (or his/her appropriate designee) will be expected to review concomitant medications with the subject at each clinical visit.

Drugs to be used with Caution with GSK1120212 and GSK2141795 are listed in Appendix F (the interactions with p450 for GSK2141795 in the in vitro studies are at much higher concentrations than with GSK1120212).

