In vitro data indicate that GSK2141795 is a CYP3A4 substrate. Drugs that potently inhibit CYP3A4 could lead to increased GSK2141795 exposure in subjects, and should either be prohibited or used with caution. Drugs which are strong inducers of CYP3A and may result in lower exposures of GSK2141795 should also be prohibited. GSK2141795 also appears to be a moderate *in vitro* inhibitor of CYP2C8 (50% inhibitory concentration [IC₅₀] 3 mcM) and CYP3A4 (IC₅₀ 11 mcM). Drugs that are substrates of CYP3A4 or CYP2C8 with a narrow therapeutic index may be prohibited. Drugs that are sensitive substrates of CYP3A4 or CYP2C8 should be used with caution.

The following medications (including but not limited to) are prohibited during the study:

PROHIBITED – highly sensitive and/or low therapeutic index CYP3A/CYP2C8/BCRP/CYP3A4 substrates since concentrations of these drugs may be increased		
CYP3A Substrate Therapeutic Area		
Cisapride	Hypnotics and Sedatives	
Pimozide	Antidepressant, Antipsychotics, Antianxiety agents	
Astemizole	Antihistamine	
BCRP Substrate		
rosuvastatin, sulfasalazine HMG-CoA Reductase Inhibitors, gastrointestinal agents		
PROHIBITED – strong inducers/inhibitors of CYP3A4		
Strong CYP3A4 Inhibitor/Inducer Therapeutic Area		
clarithromycin, telithromycin, rifamycin class agents (e.g. , rifampin, rifabutin, rifapentine), troleandomycin	Antibiotics	
itraconazole, ketoconazole	Antifungals	
Nefazodone	Antidepressants	
atazanzvir, delaviridine, indinavir, lopinavir, nelfinavir, ritonavir, saquinavir, nevirapine	Antivirals	
carbamazepine, phenobarbital, phenytoin	Anticonvulsants	

The following medications (including but not limited to) that may alter the concentrations of trametinib or GSK2141795 or have their elimination altered by trametinib or GSK2141795 should be administered WITH CAUTION:

USE WITH CAUTION – Drugs Potentially Affecting trametinib or GSK2141795 concentrations		
Drug	Therapeutic Area	
quinidine, diltiazem, verapamil	Antiarrhythmics:	
fluvoxamine, fluoxetine, paroxetine, nefazodone	Antidepressants:	
aprepitant, cimetidine	Antiemetics	
fluconazole, terbinafine, voriconazole	Antifungals	
ciprofloxacin, erythromycin, isoniazid	Anti-infectives	
mibefradil, diltiazem, verapamil	Calcium Channel Blockers	
aprepitant, oxandrolone, tizanidine, gemfibrozil Miscellaneous		
USE WITH CAUTION – Drugs that may inhibit P-gp and BCRP		
Drug	Therapeutic Area	
Valspoda	Miscellaneous	
Atorvastatin	HMG-CoA Reductase Inhibitors	

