Carvedilol	Congestive Heart Failure	
Methadone	Analgesic	
Meperidine	Narcotic	
Omeprazole	Proton Pump Inhibitor	

USE WITH CAUTION – Drugs that may have their concentrations altered by trametinib or		
GSK2141795		
repaglinide, rosiglitazone, pioglitazone Antidiabetics		
alfentanil, fentanyl	Analgesics	
Quinidine	Antiarrhythmics	
Cilostazole	Anticoagulants and Antiplatelets	
Astemizole	Antihistamines	
diergotamine, ergotamine, eletriptan	Antimigraine agents	
Pimozide	Antipsychotics	
Buspirone	Anxiolytics	
Felodipine	Calcium Channel Blockers	
sildenafil, tadalafil, vardenafil	Erectile Dysfunction agents	
cerivastatin, ovastatin, simvastatin, atorvastatin	HMG-CoA Reductase Inhibitors	
alprazolam, diazepam, midazolam, triazolam	Hypnotics and Sedatives	
cyclosporine, sirolimus, tacrolimus	Immunosuppressive agents	
Cisapride	Prokinetic agents	
cyclosporine, torsemide, chloroquine, zopiclone	Miscellaneous	
Eperenone	Selective Aldosterone Blockers	
chloroquine, zopiclone Thiazolidinediones		

The likelihood of drug-drug interactions between GSK1120212 and GSK2141795 is low because the *in vitro* IC₅₀ values for inhibition and EC₅₀ values for induction of CYP450 enzymes are 3- to 100-fold higher than the anticipated clinical C_{max} values for either drug. Further, pharmacokinetic analyses comparing steady state exposures with those following single doses will be assessed for both treatments to address this question.

Use of repaglinide, rosiglitazone and/or pioglitazone is permitted only after consultation with the Medical Monitor.

Oral steroids should be used with caution and subjects monitored for steroid-induced hyperglycemia. Short courses (up to a maximum of 14 days) of oral corticosteroids intended to treat study treatment related rash or diarrhea are allowed. Budenoside is recommended for supportive care of diarrhea. Subjects will be instructed to inform the investigator before taking any of these or any other medications. Investigators (or their appropriate designee) will be expected to review concomitant medications with the subject at each clinical visit.

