APPENDIX D: List of Prohibited Medications

The following medications, including but not limited to, are **prohibited during the study**:

PROHIBITED – highly sensitive and/or low therapeutic index CYP3A/CYP2C8/BCRP/ CYP3A4 substrates since concentrations of these drugs may be increased			
CYP3A Substrate	Therapeutic Area		
Cisapride	Hypnotics and Sedatives		
Pimozide	Antidepressant, Antipsychotics, Antianxiety agents		
Astemizole	Antihistamine		
BCRP Substrate			
rosuvastatin, sulfasalazine	HMG-CoA Reductase Inhibitors, gastrointestinal agents		
PROHIBITED – strong inducers/inhibitors of CYP3A4			
Strong CYP3A4 Inhibitor/Inducer	Therapeutic Area		
clarithromycin, telithromycin, rifamycin class agents (e.g., rifampin, rifabutin, rifapentine), troleandomycin	Antibiotics		
itraconazole, ketoconazole	Antifungals		
Nefazodone	Antidepressants		
atazanzvir, delaviridine, indinavir, lopinavir, nelfinavir, ritonavir, saquinavir, nevirapine	Antivirals		
carbamazepine, phenobarbital, phenytoin	Anticonvulsants		

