APPENDIX E: List of Cautionary Medications

Medications, including but not limited to the following, that may alter the concentrations of GSK1120212 or GSK2141795 or have their elimination altered by GSK1120212 or GSK2141795 **should be administered WITH CAUTION**.

USE WITH CAUTION – Drugs Potentially Afr concentrations	fecting GSK1120212 or GSK2141795
Drug	Therapeutic Area
quinidine, diltiazem, verapamil	Antiarrhythmics:
fluvoxamine, fluoxetine,	Antidepressants:
aprepitant, cimetidine	Antiemetics
fluconazole, terbinafine, voriconazole	Antifungals
ciprofloxacin, erythromycin, isoniazid	Anti-infectives
mibefradil, diltiazem, verapamil	Calcium Channel Blockers
aprepitant, oxandrolone, tizanidine,	Miscellaneous
USE WITH CAUTION – Drugs that may inhib	bit P-gp and BCRP
Drug	Therapeutic Area
valspoda	Miscellaneous
atorvastatin,	HMG-CoA Reductase Inhibitors
carvedilol	Congestive Heart Failure
methadone	Analgesic
meperidine	Narcotic
omeprazole	Proton Pump Inhibitor
USE WITH CAUTION – Drugs that may have GSK2141795	e their concentrations altered by GSK1120212 or
repaglinide, rosiglitazone, pioglitazone	Antidiabetics
alfentanil, fentanyl	Analgesics
quinidine	Antiarrhythmics
cilostazole	Anticoagulants and Antiplatelets
astemizole	Antihistamines
diergotamine, ergotamine, eletriptan	Antimigraine agents
pimozide	Antipsychotics
buspirone	Anxiolytics
felodipine	Calcium Channel Blockers
sildenafil, tadalafil, vardenafil	Erectile Dysfunction agents
cerivastatin, ovastatin, simvastatin,	HMG-CoA Reductase Inhibitors

alprazolam, diazepam, midazolam, triazolam	Hypnotics and Sedatives
cyclosporine, sirolimus, tacrolimus	Immunosuppressive agents
cisapride	Prokinetic agents
cyclosporine, torsemide, chloroquine,	Miscellaneous
eperenone	Selective Aldosterone Blockers
chloroquine, zopiclone	Thiazolidnediones

Use of repaglinide, rosiglitazone and/or pioglitazone is permitted only after approval of the study PI.

Oral steroids should be used with caution and subjects monitored for steroid-induced hyperglycemia. Short courses (up to a maximum of 14 days) of oral corticosteroids intended to treat study treatment related rash or diarrhea are allowed. Budenoside is recommended for supportive care of diarrhea. Subjects will be instructed to inform the investigator before taking any of these or any other medications. Investigators (or his/her appropriate designee) will be expected to review concomitant medications with the subject at each clinical visit.

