APPENDIX F: CTCAE v 4.0 Grading of Visual Changes

Visual Changes - Grading Based on NCI-CTCAE v 4.0

Grade	Description
1	Asymptomatic or symptomatic but not limiting ADL; clinical or diagnostic observations only; intervention not indicated
2	Symptomatic with moderate decrease in visual acuity (20/40 or better); limiting instrumental ADL; local or noninvasive intervention indicated (e.g., topical or oral agents)
3	Symptomatic with marked decrease in visual acuity or marked visual field defect (worse than 20/40 but better than 20/200 in the affected eye); Severe pain or medically significant but not immediately sight-threatening; operative intervention indicated; disabling; limiting self care ADL
4	Sight-threatening consequences; urgent intervention indicated; blindness (20/200 or worse) in the affected eye

Ophthalmologic Exam

Subjects are required to have a standard ophthalmic exam performed by an ophthalmologist at baseline and as clinically warranted per protocol's guidance (Refer to Section 6.3.9 for visual changes stopping criteria). The exam will include indirect fundoscopic examination, visual acuity (corrected), visual field examination, tonometry, and direct fundoscopy, with special attention to retinal abnormality that are predisposing factors for RVO or CSR.

For participants with clinical suspicion of RVO or CSR, fluorescein angiography and/or optical coherence tomography are highly recommended.

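### Section 5.3 lists four drugs as both prohibited and for use with caution, and gives strong CYP3A4 inhibitors and inducers more than one status; its appendix letters, and that in exclusion 3.2.13, are one late

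*Combined protocol and SAP*

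**What the plan says.** The co-medication rules stand in four places.

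- **Section 5.3, numbered list and narrative.** Item 3 says "All medications in Appendix E are prohibited and those listed in Appendix F are to be used with caution". The closing line of that list adds that "Drugs to be used with Caution with GSK1120212 and GSK2141795 are listed in Appendix F". The cytochrome P450 text that follows cites Appendix F twice more for cautionary drugs.
- **Section 5.3, in-text tables.** One table, headed PROHIBITED, has two parts: sensitive or low-therapeutic-index substrates, and strong CYP3A4 inducers and inhibitors. The USE WITH CAUTION tables follow. One is headed "USE WITH CAUTION – Drugs that may have their concentrations altered by trametinib or" GSK2141795. Another has the antidepressant row "fluvoxamine, fluoxetine, paroxetine, nefazodone".
- **Appendices.** Appendix D is the list of prohibited medications and holds the strong-CYP3A4 table. The next two are titled "APPENDIX E: List of Cautionary Medications" and "APPENDIX F: CTCAE v 4.0 Grading of Visual Changes".
- **Exclusion 3.2.13.** It excludes required, chronic use of strong "inhibitors or inducers of p450 CYP3A4 (see Appendix E for a table of these agents").

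**The concern.** A concomitant-medication rule has to give one answer per drug. Here labelled, operative tables give two opposite answers for four named drugs.

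The protocol's own reasons for prohibition show what is at stake. Cisapride, pimozide and astemizole are prohibited as highly sensitive and/or low-therapeutic-index "substrates since concentrations of these drugs may be increased". Nefazodone is prohibited on a different ground, as a strong CYP3A4 inhibitor or inducer, and Section 5.3 describes GSK2141795 as a CYP3A4 substrate. In a multicenter trial, one site may refuse a co-medication that another allows, with each following the text. That bears on patient safety and on consistent conduct across sites.

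**Working it through.** No design figure enters this point, so there is none to reproduce. The check compares the lists, then the narrative, then the appendix letters.

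**1. Double-listed drugs.** The PROHIBITED table in Section 5.3 names these drugs:
- Substrates: 3 CYP3A + 2 BCRP = 5.
- Strong CYP3A4 inhibitors and inducers: 6 antibiotics (counting the three rifamycin examples) + 2 antifungals + 1 antidepressant + 8 antivirals + 3 anticonvulsants = 20.
- Total: 5 + 20 = 25.

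The drugs on both this list and the caution tables of Section 5.3 are:

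| Drug | Prohibited, 5.3 | Caution, 5.3 | Prohibited, App. D | Caution, App. E |
|---|---|---|---|---|
| Cisapride | yes | yes | yes | yes |
| Pimozide | yes | yes | yes | yes |
| Astemizole | yes | yes | yes | yes |
| Nefazodone | yes | yes | yes | not shown |

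The overlap is 4 of 25 (16%). It includes all three prohibited CYP3A substrates. Nefazodone does not appear in Appendix E in the text available for this review. Its antidepressant row there ends in a comma, so text may have been lost and nothing should be inferred from the absence.

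**2. Strong CYP3A4 inhibitors and inducers as a class.** Section 5.3 states their status in several ways:
- The opening P450 paragraph has potent CYP3A4 inhibitors and inducers given with caution, because they may alter exposure to both study drugs.
- The same paragraph asks that the principal investigator be alerted if intermittent use of a strong agent is needed.
- The paragraph on GSK2141795 as victim says potent inhibitors will be either prohibited or used with caution, and strong inducers prohibited.
- The PROHIBITED table in Section 5.3, repeated in Appendix D, prohibits strong inhibitors and inducers.

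**3. Appendix letters.**

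| Where cited | Letter given | Content sought | Where it is |
|---|---|---|---|
| 5.3, item 3 | E | Prohibited list | D |
| 5.3, item 3, closing line and P450 text | F | Caution list | E |
| Exclusion 3.2.13 | E | Strong-CYP3A4 table | D |

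The same one-letter shift occurs elsewhere:
- The pill diary is cited as Appendix D (Sections 5, 5.2.1 and 5.2.2) but is C.
- The correlative studies are cited as H (Sections 8.3 and 8.7) but are G.
- The glucose diary is cited as K (footnote y of the study calendar) but is J.
- The imaging submission procedure is cited as I (Section 10.3.6) but is H.

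This pattern suggests that the references were not updated when the appendices were relettered.

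**The case against.** The best defence is that the lettering errors are clerical and reveal themselves. Section 5.3 prints both lists in full under plain headings, Appendices D and E are titled for what they hold, and nobody would take a visual grading scale for a drug list. This stands. For a drug on one list only, a careful reader can recover the intended rule, so it would be wrong to say that sites cannot tell which list governs in general.

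Two stronger readings are tempting, and the documents support neither.

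- A reader might infer that Section 5.3 bans the whole caution list, including omeprazole, fentanyl, diltiazem and atorvastatin. That follows only from item 3 read alone. The caution tables in Section 5.3 and the title and opening text of Appendix E say otherwise.
- A reader might infer that eligibility is being judged from the wrong table. Exclusion 3.2.13 is operative in its own words, and Section 5.3 restates it. Only its parenthetical reference is wrong. Registration uses a protocol-specific checklist (Section 4.2) that is not in the documents, so nothing shows that any decision rests on Appendix E.

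The defence does not reach the four drugs. Their conflict lies inside the correctly titled tables, and no clause says which list prevails. Nor can the class conflict be put down to the two agents having separate rules, because the caution sentence in the P450 text names both.

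**Conclusion.** The rules are wrong as written. This is an internal inconsistency rather than a design choice.

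The main fault is that four named drugs have two opposite statuses within Section 5.3, three of them again across Appendices D and E, and that the narrative does not give strong CYP3A4 inhibitors and inducers one status. The appendix letters are a secondary, editorial fault.

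The practical effect is confined to those four drugs and that class. How often it would arise depends on how many participants need one of these agents, which the documents do not say. The response endpoint, sample size, alpha and power in Section 14.2 are unaffected. The conclusion assumes that the table entries are as printed, and it does not rely on nefazodone's absence from Appendix E.

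**What to change.** The sponsor should reconcile exclusion 3.2.13, the list, narrative and tables of Section 5.3, and Appendices D and E, so that:

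- cisapride, pimozide, astemizole and nefazodone each carry one status wherever they appear;
- strong CYP3A4 inhibitors and inducers carry one status as a class, including how intermittent use is handled.

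Which status is right is for the sponsor to decide, and none is proposed here.

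The appendix letters in 3.2.13 and Section 5.3 should then be corrected, and every other appendix reference checked against the headings. Moving each letter back by one would not be enough: Section 6.3.7 cites Appendix I for the QTcB correction, which is Appendix K. The registration checklist should be checked against the corrected 3.2.13.

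The cost is amendment wording and the IRB approval that Section 13.1 requires. It needs no new data, visits or participants.

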5.5 Duration of Follow Up

Participants will be followed for 3 years after removal from study or until death, whichever occurs first. Participants removed from study for unacceptable adverse events will be followed until resolution or stabilization of the adverse event. Date and cause of death should be provided for participants who become deceased within the 3-year interval following removal from the study. Should a participant become pregnant while on trial, the patient will be withdrawn from the study. However, the outcome of the pregnancy and the newborn's health, if the pregnancy is carried to term, will be monitored.

6. EXPECTED TOXICITIES AND DOSING DELAYS/DOSE MODIFICATIONS

Dose delays and modifications will be made using the following recommendations. Toxicity assessments will be performed using the revised NCI CTCAE version 4. All appropriate treatment areas should have access to a copy of the CTCAE version 4, which can be downloaded at: http://ctep.cancer.gov.

If possible, symptoms should be managed symptomatically. In the case of toxicity, appropriate medical treatment should be used (including anti-emetics, anti-diarrheals, etc.).

All adverse events experienced by participants will be collected from the time of the first dose of study treatment, through the study and until the final study visit. Participants continuing to experience toxicity at the off study visit may be contacted for additional assessments until the toxicity has resolved or is deemed irreversible.

Dose Level	Trametinib Dose	GSK2141795 Dose
0 → Starting Dose	1.5 mg PO every day	50 mg PO every day
-1	1.0 mg PO every day	25 mg PO every day

NOTE: AEs occurring in participants treated with GSK2141795 + trametinib may be related to 1) overlapping toxicities between the two agents (*e.g.*, rash and diarrhea); 2) toxicities typically associated with trametinib (*e.g.*, visual disturbance) or GSK2141795 (*e.g.*, hyperglycemia or hypoglycemia). However, toxicities associated with individual agents may be potentiated in the combination, or unanticipated AEs may occur.

The dose modifications may involve one or both agents, and should be based on the nature, severity and attributions of the AEs.

